13.5.2 Other Secondary Objectives

The time until distant brain recurrence will be calculated as the time between initiation of SIMT SRS and distant recurrence of brain metastases. The time to distant brain recurrence will be censored at the time of last follow-up if the patient remains alive without distant recurrence, or will be censored at death if the patient dies without distant recurrence of brain metastases. A Kaplan-Meier estimator will be used to describe the time until distant recurrence. An estimate of the proportion of patients without distance recurrence one year after SIMT SRS treatment will be generated. The time until distant brain recurrence will also be described within diagnosis-specific subgroups.

Time to neurologic death is defined as the time between initiation of SIMT SRS and death due to neurologic causes. If a patient remains alive or dies for reasons unrelated to neurologic disease, the time to neurologic death will be censored at the time of last follow-up or death not due to neurologic causes. Analyses similar to other “time to an event” outcomes will be conducted including the generation of Kaplan-Meier curves.

The proportion of patients who experience grade 3 or worse neurologic toxicity attributable to SIMT SRS will be summarized. In addition, adverse events experienced by protocol subjects will also be summarized in several other forms to satisfy scientific and monitoring needs, as well as various regulatory reporting needs (e.g. DCI SOC, and ClinicalTrials.gov). The frequency of adverse events that are possibly, probably, or definitely related to protocol treatment will be tabulated by the maximum grade for each type of adverse event.

13.6 Exploratory Objectives

This protocol includes several exploratory objectives: (1) To describe changes in neurocognition over time, (2) To describe changes in quality of life over time, (3) To quantify treatment set-up and dosimetric data for the SIMT SRS treatment technique, (4) To describe the rate of salvage therapy, (5) To describe the prevalence of radionecrosis at the SRS site, and (6) To describe the length and intensity of steroid usage post-SRS.

13.6.1 Key Exploratory Objectives

The mean changes from baseline in neurocognition as measured by Trailmaking A and B, the MMSE and the HVLT will be summarized. Similarly, the mean changes from baseline in quality of life as measured by the FACT-Brain, will be summarized.

13.6.2 Other Exploratory Objectives

Descriptive statistics (e.g. mean, median, quantiles) will be used to describe the treatment set-up and dosimetric data associated with the SIMT SRS treatment technique. Specifically, the mean and median time to set-up of the patient's SIMT treatment will be generated. Means and medians will also describe the mean volume of brain exposed to 12Gy, the PTV dose, and the total volume of all brain metastases.

The proportion of patients who receive salvage treatment after failing SIMT SRS will be estimated, and the type of treatment received will be summarized.

Data concerning radionecrosis will be summarized at the level of a lesion, as well as the patient level. The proportion of lesions who exhibit radionecrosis after SIMT SRS treatment will be summarized. With each patient having multiple lesions, the percentage of lesions within a patient that show radionecrosis will also be summarized with medians and quantiles.

The length and dose of steroid usage post-SRS will be summarized using descriptive statistics.

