5 OBJECTIVES AND ENDPOINTS

	Objective	Endpoint	Analysis
Primary	Assess the impact of using SIMT SRS for the treatment of brain metastases on survival	Proportion of patients who live longer than predicted according to the Graded Prognostic Assessment (GPA) score	See Section 13.4
Key Secondary	Describe the time to local brain recurrence	Proportion of patients that experience local brain recurrence within 1 year of SIMT SRS treatment.	See Section 13.5.1
Other Secondary	Describe the time to distant brain recurrence	Proportion of patients that experience a new brain metastasis at a site different from the original brain metastasis site 1 year after SIMT SRS treatment	See Section 13.5.2
Other Secondary	Describe the time to death due to neurological causes	Proportion of patients who are dead within 1 year of SIMT SRS treatment due to neurologic reasons	See Section 13.5.2
Other Secondary	Describe the prevalence of significant adverse events	Proportion of patients who experience grade 3, 4, or 5 neurologic adverse events attributable to SIMT SRS	See Section 13.5.2
Key Exploratory	Describe changes over time in neurocognition	Mean changes from baseline in subscales of the Trailmaking instruments and the HLVT	See Section 13.6.1
Key Exploratory	Describe changes over time in quality of life	Mean changes from baseline in subscales of the FACT-Brain instrument	See Section 13.6.1
Other Exploratory	Quantify treatment set up and dosimetric data for this treatment technique	Mean length of time to set-up and treat patient, Volume of brain exposed to 12Gy, Mean PTV dose, Total volume of all brain metastases, conformity index, maximum dose	See Section 13.6.2
Other Exploratory	Describe the rate of salvage therapy	The proportion of patients who receive salvage treatment after failing SIMT SRS	See Section 13.6.2
Other Exploratory	Describe prevalence of radionecrosis at the SRS site	Proportion of patients with radionecrosis at the SRS site; the proportion of lesions showing radionecrosis	See Section 13.6.2
Other Exploratory	Describe length and intensity of steroid usage post-SRS	Descriptive statistics	See Section 13.6.2

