8.4 Definition of Evaluable Subjects, On Study, and End of Study

All patients who receive SIMT SRS will be included in analyses.

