10 PATIENT ASSESSMENTS

A clinical research nurse will contact each patient by telephone within 2 weeks after the SRS procedure to inquire as to the patient's health status if the patient does not have an appointment with an oncologist at DUMC within that time.

At follow-up visits patients will be evaluated as described in the Table below. Patients will be seen in clinic and undergo repeat MRI imaging as standard of care every 3 months for the first 12 months following completion of SRS and every 6 months for the following 12 months. During the follow up visits, the patient will be examined for new or recurrent neurologic signs/symptoms. On MRI, local recurrence is defined as the reappearance of a metastasis in the SRS treated field (within the 50% isodose line). Each treated lesion will be documented separately. Distant recurrence is defined as the appearance of a new brain metastasis outside the SRS field (completely outside the 50% isodose line). To be deemed a recurrence or new lesion, the lesion must measure at least 5 mm in the axial plane on MRI.

Patients with a recurrent or new lesion, who are symptomatic, may undergo a biopsy to determine if the lesion is secondary to radionecrosis or metastasis. Appropriate salvage therapy will be performed at the discretion of the treating radiation oncologist.

If on evaluation the treating physician decides not to pursue an MRI because of clinical decline, this will not be a protocol violation. The most current brain MRI will be used in the determination of local control. Conversely, if a brain MRI needs to be done at an earlier time point due to medical necessity, an MRI at that time point will also not be a protocol deviation and can be included in the data collection. Brain MRI's may be done at 3 month intervals with a one month before or after allowance.

In addition, included in the category of updated medical history is pertinent interim oncologic and medication history. A medical oncologist overseeing patient's standard of care will have been responsible for chemotherapy management as well as systemic staging scans. We will record the type and duration of systemic therapies with each visit as well as the latest information on staging scans (stable or regression vs. progression of disease).

Study Calendar

	Pre-study	During SRS	First visit post SRS (\approx 4 wks.)	Follow-up Yr.1: every 3-mos. Yr. 2: every 6-mos. (\pm 2 wks.)
Informed Consent	X			

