13.1 Analysis Sets

All patients who undergo SIMT SRS treatment will be included in both safety and efficacy analyses.

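### Radionecrosis is reported as an undated crude proportion with no rule for lesions never re-imaged, so the figure mixes true absence, early death and non-assessment

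*Combined protocol and SAP*

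**What the plan says.** **Endpoint.** The objectives table in Section 5 lists, as an other exploratory endpoint, "Proportion of patients with radionecrosis at the SRS site; the proportion of lesions showing radionecrosis". Section 13.6.2 repeats the lesion-level measure ("The proportion of lesions who exhibit radionecrosis after SIMT SRS treatment will be summarized") and adds that "the percentage of lesions within a patient that show radionecrosis will also be summarized with medians and quantiles". No time point, evaluability rule or method for incomplete follow-up is attached to any of these.

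**Denominator.** Section 13.6.2 names none. Section 8.4 says "All patients who receive SIMT SRS will be included in analyses", and Section 13.1 says "All patients who undergo SIMT SRS treatment will be included in both safety and efficacy analyses". No section limits radionecrosis to lesions that were scanned again.

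**Imaging.** Under Section 10, patients "undergo repeat MRI imaging as standard of care every 3 months for the first 12 months" after SRS, and "Brain MRI's may be done at 3 month intervals with a one month before or after allowance". The study calendar marks no MRI at the 4-week visit. Section 10 adds: "If on evaluation the treating physician decides not to pursue an MRI because of clinical decline, this will not be a protocol violation". The calendar footnote and Section 10.5 make follow-up MRI dependent on clinical indication.

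**After brain progression.** Section 10.7.1 reduces follow-up to overall survival only. Section 10.7.2 has MRI continuing every three months after early withdrawal.

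**Contrast.** Sections 13.5.1 and 13.5.2 give local recurrence, distant recurrence and neurologic death a time origin, censoring rules and Kaplan-Meier curves.

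**The concern.** Radionecrosis is found on a follow-up MRI or on a biopsy prompted by one. A treated lesion that is never scanned again can hardly be recorded as necrotic, yet under Sections 8.4 and 13.1 it stays in the denominator. There are three routes to this state: death before the first scan, a scan omitted for decline, and possible loss of MRI follow-up after progression. The third route can also cut observation short for lesions already scanned once.

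The stake is interpretability. Section 3.1 hypothesises minimal toxicity, and Section 9.3 says the doses were chosen with a low radionecrosis risk in mind. Section 3.3 plans comparison with historical data where appropriate, and its list of endpoints includes the radionecrosis rate. An undated proportion that tends to fall as early mortality or missed imaging rises cannot be set beside a series with longer survival, a fixed time point or an imaged-lesion denominator. Where assessment is missing, the error runs in the favourable direction.

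**Working it through.** The documents state no radionecrosis rate, so there is no figure to reproduce. The check has three parts.

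**1. Who can miss the first scheduled MRI through death?** The inputs are the Appendix A median survivals, a first MRI at 3 months, and the 2 to 4 month range that follows from the one-month allowance in Section 10. Exponential survival is my assumption. Share dead by month t = 1 − 2^(−t/median).

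| Median (months) | t = 2 | t = 3 | t = 4 |
|---|---|---|---|
| 3.0 | 37.0% | 50.0% | 60.3% |
| 5.5 | 22.3% | 31.5% | 39.6% |
| 9.4 | 13.7% | 19.8% | 25.5% |
| 25.3 | 5.3% | 7.9% | 10.4% |

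The shorter medians are the relevant ones for several histologies. With at least 4 metastases the count item scores 0, so lung patients can reach only the 3.0, 5.5 and 9.4 month classes, melanoma only 3.4 and 4.7, and renal only 3.3 and 7.3.

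Entry requires a life expectancy of at least 3 months and KPS of at least 70, so the 3-month column probably sits at the upper end for deaths. Section 3.2 cites a SIMT series with 60% alive at 6 months. On the same model, 1 − 0.60^(3/6) = 1 − 0.775 = 22.5% dead by 3 months. Scans omitted for decline would come on top and cannot be sized.

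**2. What does non-assessment do to the proportion?** Let N lesions be treated, u never re-imaged and x found necrotic. The all-treated proportion is x/N and the re-imaged proportion is x/(N − u). For illustration, take 40 patients with 5 lesions each, so N = 200, with u = 40 and x = 16; all but the 40 patients are assumed. Then:

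- all-treated: 16/200 = 8.0%;
- re-imaged: 16/160 = 10.0%;
- if every unseen lesion had been necrotic: (16 + 40)/200 = 28.0%.

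Without u, a reader given only 8.0% cannot recover the other two.

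**3. Is the gap in part 2 a bias?** Only to the extent that unseen lesions had necrosis. Take median 5.5 months, suppose no necrosis arises before month 3, and assume 10% among lesions imaged from then on. The all-treated proportion is (1 − 0.315) × 10% = 6.9%. If all those events fall within 12 months, the cumulative incidence with death as a competing event is the same 6.9%. On these assumptions the lower figure correctly gives the risk before death per treated patient, and 10% is the risk conditional on reaching a scan. The documents do not allow the remaining part, undetected necrosis, to be separated out.

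**The case against.** The strongest reply has four parts.

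- **The denominator is inferred.** Section 13.6.2 does not state it, and Sections 8.4 and 13.1 say which patients are analysed, not how an unassessed lesion is coded. This stands, but those sections are the only guidance given. If another denominator is intended, it still has to be written down.
- **Death is not missing data.** A patient who dies before necrosis develops did not have it. This also stands. A reader might infer from part 1 of the working that the reported rate will be 8% to 50% too low. The documents do not support that: those are modelled shares dead by 3 months, and part 3 shows that such deaths alone need cause no understatement.
- **Imaging may come earlier.** Section 10 lets medically necessary earlier MRIs enter the data, and the routine scan may be a month early. This makes the unscanned share smaller than a strict 3-month scan would imply.
- **The endpoint is low-stakes.** It is exploratory and descriptive. Grade 3 or worse neurologic toxicity attributable to SIMT SRS is a separate secondary endpoint, and radionecrosis is a listed possible side effect in Section 11.1.1. Giving secondary endpoints fuller methods is ordinary prioritisation. This stands and sets the severity.

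Sections 3.6 and 13.4.1 also doubt that radiation swelling can be told from progression without biopsy. That classification problem is separate, and a better denominator does not cure it.

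**Conclusion.** The point holds in limited form and is minor. As written, the plan gives radionecrosis as a proportion with no date and no rule for unassessed lesions, and its only analysis-set statements leave those lesions in the denominator as non-events. The figure therefore combines three different states and cannot be compared with series reported on imaged lesions or at a fixed time.

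The direction of any ascertainment error is downward; its size is unknown. The part 1 percentages rest on exponential survival at the Appendix A medians and serve only as an upper-end guide to scheduled scans missed through death. The primary decision rule of 17 or more of 40 patients in Section 13.8 is unaffected.

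**What to change.** In Section 13.6.2:

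1. Keep the all-treated proportions of lesions and patients.
2. Beside them, report the proportions among lesions and patients with at least one brain MRI after SRS, labelled as conditional on being re-imaged.
3. State the number of patients and lesions treated but never re-imaged.
4. Add a 12-month cumulative incidence of first radionecrosis per patient, with death as a competing event. Censor only patients who are alive when MRI follow-up ends. Deaths stay in as competing events: censoring everyone at the last MRI would remove them all, because every death follows the last scan. The censoring at death used in Section 13.5.1 should not be carried over, for the same reason.

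The cumulative incidence is still of detected radionecrosis, which is why item 3 is needed beside it.

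Sections 10.7.1 and 10.7.2 must be reconciled on what follow-up continues after brain progression, because the answer determines how long lesions are observed.

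The cost is a few sentences and a small table. Lesions are already tracked at each MRI (Section 9.3) and deaths are collected for survival, so no new data are needed. The downside is a smaller denominator for the re-imaged rate and a slightly less favourable figure.

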13.7 Interim Analysis

Adverse events experienced by patients will be reviewed in an aggregate manner at least annually.

13.8 Sample Size Calculation

Forty (40) patients will be accrued to this study and treated with SIMT SRS. If 17 or more of these patients live longer than expected according to the GPA score, then SIMT SRS will be considered non-inferior to historical data pertaining to survival of patients with brain metastases. With this decision rule and 40 patients, there is 90% power to detect a non-inferiority difference of -0.2 using a one-sided exact test with a target significance level of 0.10 (PASS 14, 2015). The actual significant level achieved is 0.0633.

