3.3 Design and Procedure

Forty patients with four or more brain metastases will be enrolled prior to radiosurgery. A planning MRI brain scan will be performed with GD-DPTA within one week prior to radiosurgery, per the standard of care. Patients who have completed a diagnostic MRI with contrast within 14 days of radiosurgery do not need to have a planning MRI. At that time, Neurocognitive (Mini-Mental Status Examination (MMSE), Trail-making test A&B, Hopkins Learning Verbal (HVL)) and functional assessment of cancer therapy-brain (FACT- Br) will also be obtained. Dose will be prescribed to the maximum isodose line encompassing the resulting PTV using the dose guidelines as described below.

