10.7.3 Replacement of Early Withdrawal(s)

We will accrue 40 patients and will not replace patients once the accrual process is through. We treat over 300 SRS patients a year and we estimate that we should be able to accrue to the study readily.

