13.4.2 Statistical Hypothesis, Model, and Method of Analysis

The goal of the study is to confirm that the use of SIMT SRS does not significantly reduce or compromise the prognosis of patients. Within each of 5 diagnosis groups (non-small cell lung cancer, melanoma, breast cancer, renal cell carcinoma, and GI cancer), various prognostic groups have been defined by Sperduto.¹⁶ Within each of these diagnosis-prognosis groups, an expected survival has been determined. It is hoped that the survival of patients treated with SIMT SRS is similar to or better than that seen among Sperduto's cohort. In other words, it is hoped that the survival with SIMT SRS is not inferior to that reported in the Sperduto paper.

With the expected proportion of patients living longer than expected to be 50%, a test of non-inferiority will be conducted. Details are provided in the section concerning sample size justification.

Additionally, the Kaplan-Meier estimator will be used to describe the survival of all patients treated with SIMT SRS. The survival of patients within diagnosis-specific subgroups will also be similarly described. Within the context of the Kaplan-Meier estimator, median survival, 6-month survival, and 12-month survival will be estimated. Survival is defined as the time between initiation of SIMT SRS and death, and will be censored at last follow-up if the patient remains alive.

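### The rule of 17 successes in 40 has exact power of 86.6%, not the stated 90%, and Section 13.8 gives no cut-off if fewer than 40 patients are treated

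*Combined protocol and SAP*

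**What the plan says.** Section 13.8 sets the sample size as "Forty (40) patients will be accrued to this study and treated with SIMT SRS" and the decision rule as "If 17 or more of these patients live longer than expected according to the GPA score". It claims that "there is 90% power to detect a non-inferiority difference of -0.2", "using a one-sided exact test with a target significance level of 0.10", and reports an achieved level of 0.0633. Section 13.4.2 supplies the alternative, "With the expected proportion of patients living longer than expected to be 50%, a test of non-inferiority will be conducted", and refers to the sample size section for the details of the test. Section 13.8 is therefore the only place where the rule is specified.

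Three other sections bear on how many patients enter the test:

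- Section 3.3 places enrolment before treatment: "Forty patients with four or more brain metastases will be enrolled prior to radiosurgery".
- Section 13.1 defines the analysis set by treatment received: "All patients who undergo SIMT SRS treatment will be included in both safety and efficacy analyses". Section 8.4 says the same.
- Section 10.7.3 on replacement reads: "We will accrue 40 patients and will not replace patients once the accrual process is through".

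The plan gives no expected proportion of enrolled patients who go untreated, and no cut-off for any number treated other than 40.

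**The concern.** There are two linked problems. First, the stated power does not belong to the stated rule, so anyone judging the design by Section 13.8 is given a figure that is too favourable.

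Second, the number enrolled and the number analysed are counted at different points. A patient who enrols but never receives radiosurgery counts towards the 40 of Section 3.3 and is outside the analysis set of Section 13.1. If that happens and accrual stops at 40 enrolled, the primary test has no defined cut-off. Keeping 17 would make the test stricter than its target level requires, so a non-inferior treatment could miss the criterion because a few patients went untreated. Choosing another cut-off at analysis would make the primary conclusion depend on a decision taken with the data in hand.

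**Working it through.** **Inputs**

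- Number treated n = 40 and cut-off c = 17 (Section 13.8).
- Alternative p1 = 0.50 (Section 13.4.2).
- Margin -0.20 (Section 13.8), so null p0 = 0.50 - 0.20 = 0.30.
- One-sided exact test, target level 0.10 (Section 13.8).

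**Formula**

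P(X ≥ c | n, p) = Σ C(n,k) p^k (1-p)^(n-k), summed over k = c to n. The level uses p = 0.30 and the power uses p = 0.50.

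**Step 1: the plan's own figures at n = 40**

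- Level: P(X ≥ 17 | 40, 0.30) = 0.0633. This matches Section 13.8 and confirms the reading of the null as 0.30.
- Power: P(X ≥ 17 | 40, 0.50) = 0.8659, or 86.6%. The stated 90% is not reproduced; the difference is 90 - 86.6 = 3.4 points.
- Neighbouring cut-offs do not rescue it. A cut-off of 16 gives power 92.3% but level 0.1151, above the target. A cut-off of 18 gives level 0.0320 and power 78.5%.

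No exact rule with 40 patients has both a level of at most 0.10 and power of 90%.

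**Step 2: fewer than 40 treated**

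The middle columns hold the count at 17. The right-hand columns re-derive it as the smallest c with P(X ≥ c | n, 0.30) ≤ 0.10. The values of n below 40 are assumptions that show a range.

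| n treated | Level, c = 17 | Power, c = 17 | Re-derived c | Level | Power |
|---|---|---|---|---|---|
| 40 | 0.0633 | 86.6% | 17 | 0.0633 | 86.6% |
| 39 | 0.0500 | 83.2% | 16 | 0.0944 | 90.0% |
| 38 | 0.0388 | 79.1% | 16 | 0.0762 | 87.2% |
| 37 | 0.0295 | 74.4% | 16 | 0.0604 | 83.8% |
| 36 | 0.0219 | 69.1% | 15 | 0.0917 | 87.9% |
| 35 | 0.0160 | 63.2% | 15 | 0.0731 | 84.5% |
| 34 | 0.0113 | 56.8% | 15 | 0.0571 | 80.4% |

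**Step 3: size of the loss**

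Measured from the correct 86.6%, holding 17 costs 86.6 - 83.2 = 3.4 points for one untreated patient, 86.6 - 79.1 = 7.5 for two and 86.6 - 69.1 = 17.5 for four. At n = 36 the gap between the two approaches is 87.9 - 69.1 = 18.8 points. The loss therefore comes almost entirely from keeping the count fixed, not from the smaller sample.

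**The case against.** A reader might infer that the plan insists on 17 successes whatever the number treated, that no patient is ever replaced, and that any shortfall cuts power sharply. The documents do not support this.

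- The rule in Section 13.8 is attached to 40 treated patients. It is silent about other numbers, and no section carries 17 over to a smaller sample. The same section names the test and its target level, so a statistician could reapply that test to the number treated and recover the right-hand columns of the table.
- Section 10.7.3 rules out replacement only after accrual has ended. Read with Section 13.8, accrual until 40 have been treated is a fair interpretation.
- Withdrawal after radiosurgery does not shrink the Section 13.1 analysis set. Only enrolled patients who are never treated do.
- Most patients have a single treatment session (Section 8.1.3) and the technique is already departmental practice (Section 4.3), so the shortfall may be small or nil. One missing patient costs only 3.4 points.
- Holding 17 errs on the safe side, because the level falls and a false claim of non-inferiority becomes less likely. Section 13.4.3 adds that the decision rule is not the only basis for further use.

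All of this stands, and it limits the point to an unstated rule and a wrong power figure. It does not remove either. The text leaves open which accrual reading is meant, and reapplying the test at the number treated is sensible but not written down.

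Two cautions about the remedy also stand. Part of the recovered power comes from using more of the permitted level: at n = 39, moving from 17 to 16 raises the level from 0.0500 to 0.0944, which is why power there exceeds that at n = 40. And the lower cut-offs must not be reached by excluding treated patients whose status is unknown. With 40 treated, 16 successes and one unknown, exclusion would give 16 of 39 and pass, while keeping the patient in the denominator without counting a success would give 16 of 40 and fail. Such exclusion would contradict Section 13.1 and could bias the proportion if loss to follow-up is related to prognosis.

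**Conclusion.** The power statement in Section 13.8 is wrong as it stands: 17 of 40 has exact power of 86.6% at the stated level of 0.0633. This assumes only p0 = 0.30 and p1 = 0.50, both taken from the plan.

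The second part is conditional. The rule is defined for 40 treated patients only, and the text does not settle whether 40 will be treated. Should fewer be treated and 17 be retained, the test is conservative and power falls modestly with one patient missing and substantially from about two onwards. How likely that is cannot be judged from the documents. It is an omission in specification that is worth correcting before analysis, not evidence that the design will fail.

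**What to change.** In Section 13.8:

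1. Restate the power of 17 of 40 as 86.6%, leaving the level at 0.0633.
2. State whether accrual continues until 40 patients have been treated.
3. Pre-specify the cut-off for the number treated as the smallest c with exact P(X ≥ c | p = 0.30) ≤ 0.10: 17 for 40, 16 for 37 to 39, and 15 for 34 to 36. Give the exact level and power for each, as in the right-hand columns of the table (for example, 16 of 38: 0.076 and 87.2%; 15 of 36: 0.092 and 87.9%).
4. Keep the denominator as all treated patients, as in Section 13.1, and say explicitly that treated patients of unknown status are not dropped from it.

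The cost is a short table and a few sentences, with no additional patients. The drawbacks are a less favourable stated power and a level that varies with the number treated, although it stays within 0.10.

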13.4.1 Variable

Though local control is of primary interest in this study, there is concern about the ability to differentiate between swelling due to radiation and disease progression without conducting a biopsy. The use of a biopsy to determine recurrence is not feasible given the number of brain metastases. Hence we focus on the survival of patients with brain metastases who are treated with SIMT SRS. The goal of the study is to confirm that use of SIMT SRS does not reduce the prognosis of patients.

The population of patients with brain metastases is a heterogeneous population with expected survival ranging between 3 and 25 months. We will use the expected survival defined by the diagnosis-specific GPA (Graded Prognostic Assessment) index to assess the efficacy of SIMT SRS.¹⁶ Specifically, for each patient we will determine whether the patient lives longer than expected based upon the GPA index. If the survival of patients treated with SIMT SRS is truly comparable to the survival of patients treated with currently available treatment regimens, then we would expect that approximately half of the patients would live longer than expected.

Hence, the primary endpoint of the study will be the proportion of patients who live longer than expected according to the diagnosis-specific GPA index.

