13.4.3 Inferences

This study has been designed with the best historical data currently available to assess the efficacy of SIMT SRS in a single-arm study. However, this benchmark is imperfect, and does not reflect the possible impact of rapidly emerging novel therapeutics, including immunotherapies, that target the primary disease of these patients. In addition, this benchmark does not reflect the few

patients we may have with recurrent brain metastases as the GPA scoring was developed from a database that included patients who completed brain treatment within 2 months of the diagnosis of brain metastases. If a better benchmark data becomes available during the conduct of this study, the design of this single-arm study may be modified.

Though a decision-rule is provided in section 13.8 to test the non-inferiority of SIMT SRS treatment relative to the Sperduto GPA-based benchmark, other factors will be considered in determining whether further usage of SIMT SRS is reasonable. Two important issues that will factor into this decision-making include: technical feasibility of administering SIMT SRS, and clinical factors such as neurologic control and local control.

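### Section 13.8 claims 90% power for the rule of 17 or more successes in 40 patients, but on the plan's own inputs the exact power is 86.6%

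*Combined protocol and SAP*

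**What the plan says.** The primary endpoint is the proportion of patients who outlive the survival predicted by their diagnosis-specific GPA score. Section 13.4.1 explains the benchmark: if survival with SIMT SRS is comparable to that with current regimens, "we would expect that approximately half of the patients would live longer than expected". Section 13.4.2 turns this into a planning value: "With the expected proportion of patients living longer than expected to be 50%, a test of non-inferiority will be conducted". It refers to the sample size section for the details.

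Section 13.8 gives those details. The sample size is 40. The rule is "If 17 or more of these patients live longer than expected according to the GPA score", in which case SIMT SRS is declared non-inferior. The test is one-sided and exact, with a target significance level of 0.10. Two operating characteristics are reported for this rule. One is the power: "With this decision rule and 40 patients, there is 90% power to detect a non-inferiority difference of -0.2". The other is the attained level: "The actual significant level achieved is 0.0633".

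Section 13.4.3 adds that the rule is not the only basis for a decision, since "other factors will be considered in determining whether further usage of SIMT SRS is reasonable".

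**The concern.** The significance level and the power of a fixed single-arm rule are both binomial tail probabilities for the same cut-off, one taken at the null proportion and one at the alternative. Once the sample size, cut-off, margin and expected proportion are given, neither is free. The two figures reported in Section 13.8 do not fit together: the inputs that reproduce the stated significance level give a power below the one stated.

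This is the only power statement in the plan, and it belongs to the only formal test; the other endpoints are described, not tested. A reader who has to interpret a result of 16 or fewer successes would use the implied 10% type II error to judge how likely such a result is when survival truly matches the benchmark. That error is understated.

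**Working it through.** **Inputs**

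- Sample size n = 40, pass if X ≥ 17, one-sided exact test, target significance level 0.10 (Section 13.8).
- Expected proportion p1 = 0.50 (Section 13.4.2).
- Margin −0.2 (Section 13.8), so the null boundary is p0 = 0.50 − 0.20 = 0.30.

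Section 13.8 does not itself name the proportion at which power was computed. The 0.50 is taken from Section 13.4.2.

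**Formula**

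With X binomial(40, p), the probability of passing is P(X ≥ 17 | p) = Σ C(40, x) p^x (1 − p)^(40 − x), summed over x = 17 to 40. The significance level is this sum at p = 0.30, and the power is the sum at p = 0.50.

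**Step 1: reproduce the plan's significance level**

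P(X ≥ 17 | 0.30) = 0.0633. This matches Section 13.8 to four decimals and confirms that the null boundary of 0.30 and the cut-off of 17 have been read as intended.

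**Step 2: power of the same rule**

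P(X ≥ 17 | 0.50) = 0.8659, so the type II error is 1 − 0.8659 = 0.1341. The stated 90% is 90.0 − 86.6 = 3.4 percentage points too high.

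**Step 3: would another cut-off at n = 40 give 90%?**

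| Pass mark | Significance level at 0.30 | Power at 0.50 |
|---|---|---|
| 15 | 0.1926 | 0.9597 |
| 16 | 0.1151 | 0.9231 |
| 17 | 0.0633 | 0.8659 |
| 18 | 0.0320 | 0.7852 |

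No. A mark of 16 exceeds 90% power but breaks the 0.10 target. A mark of 17 meets the target but falls short of 90%.

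**Step 4: how far would the alternative have to move?**

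| True proportion | Power with a mark of 17 |
|---|---|
| 0.49 | 0.8365 |
| 0.50 | 0.8659 |
| 0.51 | 0.8914 |
| 0.52 | 0.9133 |

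Power reaches 90% at a true proportion of about 0.514.

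**Step 5: other possible sources of the 90%**

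- *Normal approximation.* At a nominal level of 0.10, four variants give 0.9123, 0.8844, 0.8940 and 0.9304. These describe a nominal 0.10 test, not a rule with an attained level of 0.0633. For the actual rule, the continuity-corrected approximation gives 1 − Φ((16.5 − 20)/√10) = 0.8658, in agreement with the exact value.
- *Rounding.* To a whole percent, 86.6% becomes 87%. Only a proportion shown to one decimal, 0.9, would read as 90%.
- *A neighbouring sample size.* An exact test at n = 39 with a mark of 16 has level 0.0944 and power 0.9002; at n = 42 with a mark of 17 it has 0.0967 and 0.9179. Exact power does not rise steadily with n, so neither figure carries over to n = 40.

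The documents do not say which of these, if any, produced the figure.

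**The case against.** The best case on the other side concerns weight, not arithmetic. Power is a planning quantity and plays no part in the analysis: the pass mark is fixed, the attained significance level is correctly stated and lies below its target, and 86.6% is still reasonable for a 40-patient single-arm study. The shortfall reflects binomial discreteness at this particular n, as the results at n = 39 and n = 42 show, and does not mean that the trial is materially too small. The benchmark is also soft. Section 13.4.1 says only approximately half, Section 13.4.3 calls the benchmark imperfect, and a shift of 1.4 points in the true proportion would bring the power to 90%. Finally, Section 13.8 does not state the alternative, so 0.50 is inferred, and the 90% may be a coarsely rounded 0.866.

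Most of this stands as a limit on importance, and it rules out any call for redesign. It does not rescue the figure. Section 13.4.2 fixes the planning value at 50%, the reproduced 0.0633 ties the null to 0.30, and no alternative above 50% is given anywhere. Section 13.8 attaches the 90% to this rule and to an exact test, in a paragraph that reports the significance level to four decimals. However the 90% arose, it is not the power of that rule.

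**Conclusion.** The stated power is wrong as written. For 17 or more successes in 40 patients, the exact power is 86.6% against a stated 90%, and the type II error is 13.4% against an implied 10%, about one third higher (13.4/10 = 1.34). This assumes a true proportion of 0.50, from Section 13.4.2, and an evaluable primary outcome for all 40 patients. If the true proportion lies between 0.49 and 0.52, power runs from 83.7% to 91.3%.

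The error is confined to one planning figure. The type I error, the pass mark and the validity of the test are unaffected, and Section 13.4.3 already provides for weighing other evidence alongside the rule. It should be corrected because it is the trial's only power claim and is likely to be repeated in reports.

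**What to change.** Replace the power and significance-level sentences in Section 13.8 with one that names the alternative, for example: *With 40 patients and a threshold of 17, the exact one-sided significance level is 0.063 against a null proportion of 30%, and the power is 87% if the true proportion is 50%.* Keep the target level of 0.10 as the design criterion.

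The cost is one sentence. The sample size, pass mark, analysis set and significance level do not change. The stated power becomes slightly less favourable.
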